5. End of the Assessment Period (Visit 5, Week 12):

The following procedures/assessments must be completed:

- Recording of concurrent diseases and medical conditions.
- Recording of concomitant medications.
- Physical examination and vital signs.
- BP measurement.

RENARIN	Glol	bal Medical Department	
	Protocol Template		
Identification Number	Version Number	State	Effective date
FORM-000050125	3.0, CURRENT	Effective	13 May, 2022

- ECG.
- Laboratory tests (a follow-up phone call will be made within 24 hours in case of any clinically significant abnormality from the laboratory tests according to the Investigator).
- UPT (only for female patients).
- Adherence assessment by return of NEB and RAM tablets (also empty blisters) and accountability.
- Assessment of AES and SAEs (In case of any patients having an ongoing AE or SAE at the end of the treatment, there will be a follow-up telephone call after 2 weeks to ensure patient safety).
- Return of written instruction for self BP measurement and patient diary dispensed at Visit 4 to the site.
- Return of BP device (dispensed at Visit 1) to the site.

RENARIN	Global Medical Department Protocol Template		
Identification Number	Version Number	State	Effective date
FORM-000050125	3.0, CURRENT	Effective	13 May, 2022

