Statistical Assumptions	The primary endpoint will be assessed before and after Assessment period at Week 12, by a paired t-test using the Modified Intent-to-Treat population and the Per-Protocol population. A sample size of 215 achieves 90% power to detect a Systolic BP difference of -2.4 mmHg between the null hypothesis mean of 3.0 mmHg and the alternative hypothesis mean of 5.4 mmHg with a known standard deviation of 12.0
	mmHg and with a significance level (alpha) of 0.05 using a one-sided

NENARINI	Glo	bal Medical Department	
	Protocol Template		
Identification Number	Version Number	State	Effective date
FORM-000050125	3.0, CURRENT	Effective	13 May, 2022

Γ	
	one-sample t-test. Assuming an approximate 20% screen failure/drop-
	out rate, two-hundred and seventy (270) patients with uncontrolled
	hypertension are planned to be screened to obtain at least 215 completed
	patients at the end of the study (Visit 5) (patients who complete all visits
	including EoS Visit [Visit 5]). Hypothesis about the direction of the
	treatment effect: one-sided test has more statistical power to detect an
	effect in one direction because it is expected that combination therapy
	increases treatment efficacy in patients with uncontrolled hypertension
	previously treated with NEB or RAM monotherapies for at least 30 days.
	In this scenario, it is possible to exclude the hypothesis of testing the
	possibility that the combination therapy is less effective than the
	monotherapy, for this reason a one-sided test is more appropriate.

NENARINI	Glo	bal Medical Department	
	Protocol Template		
Identification Number	Version Number	State	Effective date
FORM-000050125	3.0, CURRENT	Effective	13 May, 2022

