5 STUDY DESIGN

This is a Phase IV, interventional, multicenter, open-label, multinational study with 2 study periods (a Run-in period of 4 weeks and an Assessment period of 12 weeks) to assess the efficacy and safety of the extemporaneous combination of NEB and RAM in reducing SBP and DBP in hypertensive patients uncontrolled by monotherapy.

The trial will be conducted in approximately 26 investigational clinical sites in Bulgaria, Poland, and Hungary. The total study duration is 16 weeks including a Run-in period of 4 weeks and an Assessment period of 12 weeks.

Note: For the purpose of this study, uncontrolled BP is defined as sitting SBP/DBP:

- \geq 130/80 mmHg in patients < 65 years old
 - \geq 140/80 mmHg in patients \geq 65 years old

Screening Visit 1 (Week -4):

Hypertensive patients with SBP ranging from ≥ 140 to ≤ 179 mmHg and/or DBP ranging from ≥ 90 to ≤ 109 mmHg on treatment, for at least 30 days prior to screening, with NEB 5 mg or any other BB, or RAM 5 mg or any other ACE-i will be screened for eligibility (Visit 1). Patients that did not meet eligibility criteria will be considered as screening failures and will not be re-screened.

Run-in period from Visit 1 (Week -4) to Visit 2 (Week 0):

On the same day of the Screening Visit, eligible patients will enter a Run-in period, during which:

- Patients receiving NEB 5 mg or RAM 5 mg will continue the same therapy for 4 weeks.
- Patients on any other BB will be assigned to monotherapy with NEB 5 mg while patients on any other ACE-i will be assigned to monotherapy with RAM 5 mg for 4 weeks.

The study is designed in order to ensure that 1:1 ratio between patients in the NEB and RAM arms will be achieved. For details see Section 5.

Assessment period from Visit 2 (Week 0) to Visit 5 (Week 12):

After 4 weeks (\pm 2 days) of the Run-in period of monotherapy (Week 0), BP will be further assessed at Visit 2.

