Patients with uncontrolled BP levels (sitting BP \geq 130/80 mmHg in patients < 65 years old/sitting BP \geq 140/80 mmHg in patients \geq 65 years old) at Visit 2, with adequate treatment adherence (ranging between 80% to 120%) and who did tolerate the treatment, will enter into the Assessment period and will be assigned to the extemporaneous combination of NEB/RAM 5/2.5 mg. Patients with controlled BP levels (sitting BP < 130/80 mmHg in patients < 65 years old/sitting BP < 140/80 mmHg in patients \geq 65 years old) and/or who do not tolerate the treatment or have an adherence range below 80% or above 120%, will be withdrawn from the study (drop-out patients).

CONFIDENTIAL

MENARINI	Global Medical Department		
	Protocol Template		
Identification Number	Version Number	State	Effective date
FORM-000050125	3.0, CURRENT	Effective	13 May, 2022

After 4 weeks \pm 2 days in the Assessment period (Week 4), patients BP will be further evaluated at Visit 3: patients with controlled BP levels (sitting BP < 130/80 mmHg in patients < 65 years old/sitting BP < 140/80 mmHg in patients \geq 65 years old) will continue the same extemporaneous combination, while patients with uncontrolled BP levels (sitting BP \geq 130/80 mmHg in patients < 65 years old/sitting BP \geq 140/80 mmHg in patients \geq 65 years old) will be up-titrated from NEB/RAM 5/2.5 mg to NEB/RAM 5/5 mg for further 4 weeks \pm 2 days.

After further 4 weeks \pm 2 days (Week 8) the BP will be assessed again (Visit 4): controlled patients will continue the same extemporaneous combination, while uncontrolled patients:

- if on NEB/RAM 5/2.5 mg, will be up-titrated to NEB/RAM 5/5 mg for further 4 weeks ± 2 days (Visit 5, Week 12);
- if on NEB/RAM 5/5 mg, will be up-titrated to NEB/RAM 5/10 mg for further 4 weeks ± 2 days (Visit 5, Week 12).

At the end of the Assessment period (12 weeks \pm 2 days), at Visit 5, the antihypertensive effect of the extemporaneous combination (NEB/RAM 5/2.5 mg, NEB/RAM 5/5 mg or NEB/RAM 5/10 mg) will be evaluated.

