To correctly evaluate the additional effect of the combination therapy, the number of patients with uncontrolled BP on NEB or RAM monotherapy needs to be balanced at Visit 2. To maintain a 1:1 ratio during the Assessment period, a cap of 110 patients for each treatment arm (i.e., NEB and RAM) will be included at Visit 2 to maintain a balanced number of uncontrolled patients entering the Assessment period for each drug. The evaluation will be done every 50 patients. If the entrance in the Assessment period for 1 of the 2 tested drugs will deviate more than 5%, a corrective measure will be initiated: according to the enrolment site statistics, 1 or more sites will be informed to enroll a greater number of patients being treated with the least represented drug in the Assessment period.

A total number of 270 patients will be screened considering a screen failure/drop-out rate of 20%, to obtain at least 215 completed patients at the end of the study (Visit 5) (patients who complete all visits including EoS Visit [Visit 5]).

Sitting BP will be measured at all visits before blood sampling. Blood Pressure will be measured in both arms at the Screening Visit (Visit 1) to detect possible between-arm differences. Three BP measurements will be performed for each arm. The arm with the higher mean DBP will be identified at screening and will be used in all subsequent visits for BP assessment. Blood pressure measurements should be performed as nearly as possible within the same time frame of the day (7:00 a.m. to 12:00 p.m.), on the same arm, possibly by the same trained member of the site staff/personnel and using the same calibrated automated device, provided by the Sponsor, at each visit.

Patients should be seated comfortably in a quiet environment for 5 minutes before beginning BP measurements. Three BP measurements will be recorded, 1 to 2 minutes apart, and CONFIDENTIAL Page 36 of 90

RENARIN	Glot	bal Medical Department	
	Protocol Template		
Identification Number	Version Number	State	Effective date
FORM-000050125	3.0, CURRENT	Effective	13 May, 2022

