Each trial participant is provided with 1 treatment Patient Kit made up by:

- NEB 5 mg: 1 box containing nebivolol 5 mg 42 tablets (3 blisters with 14 tablets).
- RAM 2.5 mg: 1 box containing ramipril 2.5 mg 42 tablets (3 blisters with 14 tablets).

The 2 boxes are then sealed together into a transparent plastic film to realize the treatment patient kit.

Trial participant must be carefully instructed by Investigator or designee to take simultaneously (at the same time): NEB 5 mg as one white round tablet and RAM 2.5 mg as one yellowish oblong tablet, according to Study Protocol.

REVARIN	Global Medical Department		
		Protocol Template	
Identification Number	Version Number	State	Effective date
FORM-000050125	3.0, CURRENT	Effective	13 May, 2022

Visit 3 (Assessment Period):

Participants with controlled BP are provided with 1 treatment Patient Kit made up by:

- NEB 5 mg: 1 box containing nebivolol 5 mg 42 tablets (3 blisters with 14 tablets).
- RAM 2.5 mg: 1 box containing ramipril 2.5 mg 42 tablets (3 blisters with 14 tablets). The 2 boxes are then sealed together into a transparent plastic film to realize the treatment Patient Kit.

Trial participant must be carefully instructed by Investigator or designee to take simultaneously (at the same time): NEB 5 mg as one white round tablet and RAM 2.5 mg as one yellowish oblong tablet, according to Study Protocol.

Participants with uncontrolled BP are provided with 1 treatment patient kit made up by:

- NEB 5 mg: 1 box containing nebivolol 5 mg 42 tablets (3 blisters with 14 tablets).
- RAM 5 mg: 1 box containing ramipril 5 mg 42 tablets (3 blisters with 14 tablets).

The 2 boxes are then sealed together into a transparent plastic film to realize the treatment patient kit.

Trial participant must be carefully instructed by Investigator or designee to take simultaneously (at the same time): NEB 5 mg as one white round tablet and RAM 5 mg as one light red oblong tablet, according to Study Protocol.

Visit 4 (Assessment Period):

Participants with controlled BP who were on NEB/RAM 5/2.5 mg are provided with 1 treatment Patient Kit made up of:

• NEB 5 mg: 1 box containing nebivolol 5 mg 42 tablets (3 blisters with 14 tablets).

• RAM 2.5 mg: 1 box containing ramipril 2.5 mg 42 tablets (3 blisters with 14 tablets). The 2 boxes are then sealed together into a transparent plastic film to realize the treatment patient kit.

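### For patients from the ramipril run-in, the Week 4 change reflects nebivolol added while ramipril is halved, and no planned efficacy analysis separates the two run-in drugs

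*Protocol*

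**What the plan says.** **Run-in (Protocol 5).** "Patients receiving NEB 5 mg or RAM 5 mg will continue the same therapy for 4 weeks". Patients on another beta blocker move to NEB 5 mg, and "patients on any other ACE-i will be assigned to monotherapy with RAM 5 mg for 4 weeks". Every patient therefore reaches Visit 2 on NEB 5 mg or RAM 5 mg.

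**Visit 2 (Protocol 5).** Patients who are uncontrolled, adherent and tolerant "will enter into the Assessment period and will be assigned to the extemporaneous combination of NEB/RAM 5/2.5 mg". There is no exception by run-in drug. The single Visit 2 kit in Protocol 7.1 confirms this: with the nebivolol box it holds "RAM 2.5 mg: 1 box containing ramipril 2.5 mg 42 tablets (3 blisters with 14 tablets").

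**Later visits (Protocol 5 and 7).** RAM 5 mg becomes available from Visit 3 and RAM 10 mg from Visit 4, each only for patients still uncontrolled. Controlled patients stay where they are.

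**Stated purpose.** Protocol 5 explains the 1:1 balance of run-in drugs with the words "To correctly evaluate the additional effect of the combination therapy", and sets "a cap of 110 patients for each treatment arm (i.e., NEB and RAM) will be included at Visit 2". SAP 3.1 repeats both. Protocol 8.1 describes efficacy as a comparison with each monotherapy after 12 weeks. The synopsis, arguing for a one-sided test, sets aside the "possibility that the combination therapy is less effective than the" monotherapy.

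**Analysis.** Visit 2 is the baseline for combination analyses (SAP 6.2). SAP 16.1.3 and 16.2.1.1 to 16.2.1.3 test changes from Visit 2 with one paired test over all patients.

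**The concern.** The same prescription at Visit 2 is a different change of treatment in each half of the entrants. After nebivolol it is a true add-on. After ramipril it is an addition and a reduction together. The first up-titration then only brings this second group back to its run-in ramipril dose, and those controlled at Visits 3 and 4 remain on half of it to Week 12.

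The pooled Week 4 SBP and DBP changes are named secondary endpoints and average these two contrasts. A report that follows the protocol's language of additional effect could present the ramipril group's Week 4 result as the gain from adding nebivolol to RAM 5 mg. No reading at that visit measures this. The trial also takes trouble to balance enrolment by run-in drug and then plans no efficacy output that uses the balance.

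**Working it through.** **1. Dose behind each reading.** Protocol 5.1 places BP measurement before dispensing and before the clinic dose, so each reading reflects the preceding interval.

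| Reading | After NEB run-in | After RAM run-in | Ramipril relative to run-in, RAM group |
|---|---|---|---|
| Visit 2 (baseline) | NEB 5 | RAM 5 | 1 |
| Visit 3 (Week 4) | NEB 5/RAM 2.5 | NEB 5/RAM 2.5 | 2.5/5 = 0.5 |
| Visit 4 (Week 8) | 5/2.5 or 5/5 | 5/2.5 or 5/5 | 0.5 or 1 |
| Visit 5 (Week 12) | 5/2.5, 5/5 or 5/10 | 5/2.5, 5/5 or 5/10 | 0.5, 1 or 2 |

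At Visit 3 the whole RAM group is below its run-in dose. By Visit 5 it is a mixture, and dose depends on earlier response.

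**2. Share affected.** 110/(110 + 110) = 50% of entrants. This is the design target, not a guaranteed split.

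**3. Effect on the Week 4 mean.** Count falls in BP as positive.

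- A_N is the fall from adding RAM 2.5 mg to NEB 5 mg.
- A_R is the fall from adding NEB 5 mg to RAM 5 mg.
- d is the part of A_R lost because ramipril is at 2.5 mg instead of 5 mg.
- w is the RAM share.

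The RAM-group change is A_R − d. The pooled change is (1 − w)A_N + w(A_R − d), which is the average add-on effect minus w·d.

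The documents give no value for d. Over an assumed range with w = 0.5:

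| d (mmHg) | RAM-group reduction | Pooled reduction, 0.5 × d |
|---|---|---|
| 0 | 0 | 0 |
| 1 | 1 | 0.5 |
| 2 | 2 | 1.0 |
| 3 | 3 | 1.5 |

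No such formula applies at Weeks 8 and 12, because dose then follows response. At Week 12 a dose above run-in works in the opposite direction.

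**4. Does any planned analysis separate the groups?**

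- The paired tests pool all patients.
- The mixed model in SAP 16.1.4 uses visit, age, gender, BMI and baseline SBP with interactions. SAP 7.1 lists treatment as a factor, but it enters no model.
- SAP 16.2.1.4 and 16.2.1.5 compare patients by current combination dose.
- The prior-therapy split in Protocol 12.4 and SAP 16.3.1 is continued versus switched, and each category contains both drugs.
- The SAP 7.5 subgroups are hypertension grade, CHD, diabetes and hypercholesterolemia.
- SAP Appendix 1 shows monotherapy columns by drug and combination columns by dose, so run-in drug is not carried into the combination phase.

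The table shells are a separate document and were not available.

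**5. The plan's own sample size.** It concerns only the Week 12 primary endpoint, and it reproduces: [12.0 × (1.645 + 1.282)/2.4]² = 214.1, so 215 (one-sided 0.05, 90% power, known SD). No power is stated for Week 4.

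**6. Precision of a split.** With the protocol's SD of 12.0 mmHg and about 215/2 ≈ 107 completers per run-in drug, the 95% CI half-width for the SBP change is about 1.98 × 12/√107 = 2.3 mmHg.

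**The case against.** The strongest reply is that the comparison is coherent as it stands. The objectives speak of the antihypertensive efficacy of the combination, and regimen versus prior monotherapy is a proper contrast in both groups. The phrase about additional effect explains why enrolment is balanced. It is tied to no visit and does not say that the effect is added to RAM 5 mg. The comparison with each monotherapy in Protocol 8.1 refers to Week 12. Moving from 5/2.5 to 5/5 mg is up-titration relative to the current combination. The starting dose is a clinical choice, and halving ramipril would, taken alone, make the Week 4 fall smaller.

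Most of this stands, and it limits the point to labelling and reporting. It does not explain why run-in drug is balanced and then left out of every efficacy analysis, or what additional effect means for a patient whose ramipril was reduced.

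A reader might also infer four stronger things that the documents do not support:

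- **That a worse result on the combination is excluded from testing.** The synopsis argues this way for the sample size, but Protocol 12.5 makes the secondary BP comparisons two-sided. SAP 6.5 sets two-sided tests as the default, and SAP 16.1.3 gives a two-sided p-value for the primary analysis.
- **That the Week 4 shift can be judged against the 2.4 mmHg planning difference.** That figure belongs to Week 12 SBP, and the size of the shift is itself assumed.
- **That half the trial's duration is affected.** The half is a share of entrants.
- **That the observed change otherwise measures a clean add-on effect.** This is a single-arm, open-label study in which an uncontrolled reading at Visit 2 is both the entry condition and the baseline. Regression to the mean would push the change the other way, so the net direction is not known.

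**Conclusion.** The point holds as one of interpretation and reporting. It does not make the primary analysis invalid. For about 50% of entrants by design, the Week 4 contrast is RAM 5 mg to NEB 5 mg/RAM 2.5 mg, and it cannot be read as an effect added to RAM 5 mg. At Week 8 the same group is below or equal to its run-in ramipril dose, and at Week 12 below, equal or above, so those changes are regimen effects as well.

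The dose facts and the 50% share come from the documents. The magnitude does not: 0 to 1.5 mmHg in the pooled Week 4 mean, and 0 to 3 mmHg in the ramipril group, rest on an assumed loss of 0 to 3 mmHg that includes zero. Taken alone, this effect is conservative at Week 4. The absence of a split by run-in drug is established for the protocol and SAP. It would need checking against the table shells.

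**What to change.** 1. In SAP 16.1.3 and 16.2.1.1 to 16.2.1.3, add the Visit 2 to Visit 3, 4 and 5 changes in SBP and DBP, with 95% CIs, separately for patients from the nebivolol and the ramipril run-in. Keep the pooled test as primary, and treat the split as estimation without further tests.
2. Label each contrast by its doses. At Week 4 these are NEB 5 to NEB 5/RAM 2.5 and RAM 5 to NEB 5/RAM 2.5. At Weeks 8 and 12, state the mix of ramipril doses in each group.
3. Reconcile with the doses given: the text on additional effect (Protocol 5, SAP 3.1), the comparison with each monotherapy (Protocol 8.1) and the one-sided rationale (Protocol synopsis).
4. State that no claim of effect added to RAM 5 mg will be made from readings taken on RAM 2.5 mg.

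A table of the ramipril group by current versus run-in dose is optional and descriptive only. All three categories can occur only at Visit 5, where dose follows earlier response.

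The cost is some wording and a few table rows from data already collected, with matching shells (SAP 4 ties shell changes to a SAP amendment). No change to dosing is proposed, and no view is taken on the starting dose.

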6 SELECTION OF SUBJECTS

6.1 Informed Consent Process

Prior to the patient's enrolment into the study and before performing any study-related procedures, the Investigator - or its authorized delegate - shall obtain the patient's written, dated and signed informed consent to participate into the study and to the confidential disclosure, processing and transferring necessary documentation of the patient's health and personal data to the Contract Research Organization (CRO), Sponsor and its Affiliates, the competent Health Authorities (HA) and any other institutions, as legally required and in accordance with the local applicable privacy laws (for the privacy information to be reported on the Informed Consent Form (ICF) refer to Section 17).

Institution and Investigator undertake to duly inform patients about personal data processing and the relevant applicable privacy rights before their participation into the study.

After being duly informed and interviewed by the Investigator, the patient freely has to date and sign the ICF before being enrolled into the study and before undergoing any study procedure. The Investigator must store the original of the signed ICF in the Investigator's File, and the patient will be provided with a copy of it.

If a Protocol Amendment would affect the terms of the ICF, it will be revised to reflect the protocol change and submitted to Ethics Committee (EC) for approval.

The Investigator will ensure that this new consent form is signed by all patients subsequently entered in the study and those currently in the study, if affected by the amendment.

6.2 Inclusion and Exclusion Criteria

6.2.1 Inclusion Criteria

Patient will be considered eligible to be enrolled in the study only if he/she meets all the following inclusion criteria:

- 1. Willing to comply with all study activities and procedures for the duration of the study and provided signed, written informed consent prior to any study procedures at Screening Visit.
- 2. Male or female patients aged ≥ 18 years with hypertension with mean sitting SBP ≥ 140 mmHg and ≤ 179 mmHg and/or mean sitting DBP ≥ 90 mmHg and ≤ 109 mmHg at Visit 1 (screening), while on monotherapy treatment either with BBs (NEB 5 mg or any dose if other BB) or ACE-is (RAM 5 mg or any dose if other ACE-i) for at least 30 days before Visit 1 (screening) and, as per Investigator's judgement, is deemed appropriate for a combination treatment with BB and ACE-i.
- 3. Ability to take oral medication and willing to adhere to the drug regimen.

RENARIN	Glol	oal Medical Department	
	Protocol Template		
Identification Number	Version Number	State	Effective date
FORM-000050125	3.0, CURRENT	Effective	13 May, 2022

- 4. Female patient of childbearing potential is eligible to participate if she is not pregnant, or not breastfeeding. A woman is considered fertile following menarche and until becoming postmenopausal unless permanently sterile. Women of childbearing potential must agree to use of highly effective contraception (e.g., method of birth control throughout the study period and for 4 weeks after study completion defined as a method which results in a failure rate of less than 1% per year) and also must refrain from donating or storing eggs during this time. Highly effective contraception methods can be:
 - Combined hormonal contraception (estrogen- and progestogen-containing) associated with inhibition of ovulation (oral, intravaginal, and transdermal).
 - Progestogen-only hormonal contraception associated with inhibition of ovulation (oral, injectable, and implantable).
 - Intrauterine device.
 - Intrauterine hormone-releasing system.
 - Bilateral tubal occlusion.
 - Vasectomized partner (procedure conducted at least 2 months before the screening), (provided that partner is the sole sexual partner of the trial participant and that the vasectomized partner has received medical assessment of the surgical success).
- 5. A male patient must agree to use contraception during the whole study period and for at least 1 week after the last dose of study treatment and refrain from donating sperm during this period.

